1. SYNOPSIS

| |
|--------------------------------------------------------------------------------------------------------------------------------------------------------------------------------------------------------------------------------------------------------------------------------------------------------------------------------------------------------------------------------------------------------------------------------------------------------------------------------------------------------------------------------------------------------------------------------------------------------------------------------------------------------------------------------------------------------------------------------------------------------------------------------------------------------------------------------------------------------------------------------------------------------------------------------------------------------------------------------------------------------------------------------------------------------------------------------------------------------------------------------------------|
| Name of Sponsor/Company: Imperial College. |
| Name of Finished Product: [¹⁸ F]fluoroethyltriazole[Tyr ³]Octreotate ([¹⁸ F]-FET-βAG-TOCA) Injection |
| Name of Active Ingredient: [¹⁸ F]-FET-βAG-TOCA |
| Title of Study: Evaluation of [¹⁸ F]fluoroethyltriazole[Tyr ³]Octreotate analogues for the imaging of neuroendocrine tumours. |
| Investigators and Study Centre(s): Imanova. |
| Phase of Development: Phase 1 |
| Primary Objective: To evaluate the utility of the [¹⁸ F]fluoroethyl triazole labelled [Tyr ³]Octreotate analogue, [¹⁸ F]-FET-βAG-TOCA, in the accurate localisation of tumours in patients with a histologic diagnosis of NETs of any site. |
| Study Design: |
| Primary Endpoint: To determine the biodistribution of [¹⁸ F] following single i.v. administration of [¹⁸ F]-FET-βAG-TOCA injection To assess tumoural uptake of [¹⁸ F]-FET-βAG-TOCA |
| Safety Endpoint: The occurrence of one or more treatment-emergent adverse events (AEs) from administration of [¹⁸ F]-FET-βAG-TOCA Injection throughout the study period, and changes in serum biochemistry, haematology, coagulation, immunology, urinalysis, vital signs, ECG, injection site, and physical examination findings. |
| Selection of Subjects: |
| Main Inclusion Criteria: 
1. Written informed consent2. Age \geq 18 years3. Histological diagnosis of NET of any site, except where ENETS criteria does not mandate histology for confirmation of diagnosis or patients who have a positive ⁶⁸Gallium-peptide scan in whom NET diagnosis is pre-operatively definitive.4. Locally advanced or metastatic disease5. Eastern Cooperative Oncology Group (ECOG) performance status of ≤ 2 (appendix A)6. Life expectancy > 3 months7. Measurable disease defined as a lesion that can be accurately measured in at least one dimension with the longest diameter ≥ 10mm using conventional techniques8. Somatostatin receptor imaging within 6 months. (if patient does not have somatostatin receptor imaging they may also be included provided they have measurable disease (≥ 10mm) on conventional imaging.9. Adequate organ system function as defined in Table 1 |
| Main Exclusion Criteria: 
• Patients received chemotherapy within 3 weeks of study or radiotherapy within 4 weeks of study• Active uncontrolled infections, gastrointestinal disease, haemolysis or any serious co-existing medical illness• Psychological, familial, sociological or geographical condition potentially hampering compliance with the study protocol and follow-up schedule• Pregnant or lactating women• Females of childbearing potential who are unwilling to avoid pregnancy, for the duration of the study• Presence of any underlying medical conditions which in the investigators opinion would make the patients unsuitable for treatment• Satisfactory baseline haematologic and organ function Patient not expected to be able to tolerate the scanning sessions |
| Number of Patients Planned: 56 patients with diagnosis of neuroendocrine tumours of any site |

Treatment of Subjects:

Investigational Tracer: Subjects will receive a single i.v. bolus injection of 1-10 mL of [¹⁸F]-FET- β AG-TOCA injection over a period of at least 30 seconds. The tracer injection will be followed by a saline flush. Patients will receive a maximum ¹⁸F activity of 165 MBq.

Statistical Methods and Planned Analysis:

Using results of dynamic scanning and metabolite analysis an appropriate protocol will be designed to analyse the diagnostic static scans. The internal radiation dosimetry as well as biodistribution of the tracer will be calculated. Comparison between FET- β AG-TOCA PET and standard of care somatostatin receptor imaging will be made based on

both a per-patient and per-lesion based analysis. Non-parametric McNemar test with Bonferroni correction for multiple comparison will be used. The association between SSTR1-5 expression and imaging parameters obtained will be assessed. Data will be analysed using SPSS 16.0 for Windows.

Bio-distribution and Radiation Dosimetry

Bio-distribution data in patients will consist of ¹⁸F activity content in organs and tissues of interest, ¹⁸F activity

concentrations in whole blood and plasma and of ¹⁸F activity excreted in the urine. Descriptive statistics will be generated for bio-distribution data at each time point for each organ and tissue of interest. The amount of ¹⁸F activity excreted in urine in patients will be calculated from the product of concentration of ¹⁸F activity measured in each sample and the volume of each sample for a subset of patients.

Safety

Safety parameters will be summarized using descriptive statistics

TABLE OF CONTENTS

| | |
|-------------------------------------------------------------------------------------------------------------------------------------------------------------------------------------|-------------------------------------|
| 1. SYNOPSIS | 4 |
| 2 Table of contents..... | 6 |
| 3. LIST OF ABBREVIATIONS and Definitions of Terms | 9 |
| 4. SUMMARY | 10 |
| 4.1 Cohort 1. | 10 |
| 4.2 Cohort 2. | 11 |
| 5. BACKGROUND | 12 |
| 5.1 $[^{18}\text{F}]\text{-FET-}\beta\text{AG-TOCA-PET}$ | 14 |
| 5.2 Rationale and evidence to date | 15 |
| 6. STUDY OBJECTIVES | 16 |
| 6.1 Primary objective | 16 |
| 7. STUDY ENDPOINTS | Error! Bookmark not defined. |
| 7.1.1 Primary | 17 |
| 7.1.2 Translational end-points | 17 |
| 7.2 Cohort 2..... | 17 |
| 7.2.1 Primary | 17 |
| 7.2.2 Secondary..... | 17 |
| 7.2.3 Translational end-points | 18 |
| 8. STUDY OUTLINE..... | 18 |
| 8.1 Study design and rational of the chosen approaches | 18 |
| 8.1.1 Cohort 1. Dosimetry and safety study in patients with histological diagnosis of NETs of any site. | 18 |

3. LIST OF ABBREVIATIONS and Definitions of Terms

| | |
|-------------------|----------------------------------------------------------------------------------------------------------------------------|
| ¹⁸ F | Fluorine with an Atomic Mass of 18 |
| ⁶⁸ Ga | Gallium with an Atomic Mass of 68 |
| ^{99m} Tc | Metastable Technetium with an Atomic Mass of 99 |
| AE | Adverse Event |
| ARSAC | Administration of Radioactive Substances Advisory Committee |
| Bpm | Beats per Minute (Heart Rate) |
| CRF | Case Report Form |
| CT | Computed Tomography |
| ECG | Electrocardiogram |
| ECOG | Eastern Cooperative Oncology Group |
| ED | Effective Dose (ie, the sum of risk weighted organ absorbed radiation dose used as a measure of stochastic radiation risk) |
| EUC | Electrolytes, Urine, Creatinine |
| GCP | Good Clinical Practice GLP |
| | Good Laboratory Practice |
| GMP | Good Manufacturing Practice |
| ICH | International Conference on Harmonisation |
| IHC | Immunohistochemistry |
| i.v. | Intravenous |
| MBq | Megabecquerel |
| MHRA | Medicines & Healthcare products Regulatory Agency |
| MIRD | Medical Internal Radiation Dose |
| NET | Neuroendocrine tumour |
| PET | Positron Emission Tomography |
| PK | Pharmacokinetics |
| SAE | Serious Adverse Event |
| SRS | Somatostatin Receptor Scintigraphy |
| SSTR | Somatostatin Receptor |

[figure not shown]
4. SUMMARY

4.1 Cohort 1. Dosimetry and safety study in patients with histological diagnosis of NETs of any site.

*For safety parameters please refer to the study schedules of events, Table 1 & Table 2

4.2 Cohort 2. Open label study comparing [¹⁸F]-FET-βAG-TOCA – PET with [⁶⁸Ga]-DOTATATE-PET/CT in patients with histological diagnosis of NETs of any site.

*For safety parameters please refer to the study schedules of events, Table 1 & Table 3

5. BACKGROUND

Neuroendocrine tumours (NETs) are tumours derived from enterochromaffin cells, which are characterised by the presence of neurosecretory granules composed of a variety of hormones and biogenic amines. These tumours can release vasoactive substances into the systemic circulation, resulting in episodic flushing, wheezing, diarrhoea, and eventual right-sided valvular heart disease. All of these symptoms negatively impact on patients' quality of life. NETs can originate at any site, however the common site of disease is the midgut comprising of 40% to 70% of all NETs¹. Whilst initially thought to be relatively rare, it is evident from the US Surveillance Epidemiology and End Results database that the incidence and prevalence has increased substantially (approximately 500%) over the past 30 years, and unlike most other solid tumours, the incidence continues to rise². Within the UK 3000 patients are diagnosed each year making it the 11th most common cancer in the UK, and the second most prevalent tumour of the gastrointestinal tract.

The management of NETs is primarily determined by the stage of the disease. For patients with localised or limited disease the primary modality of therapy is surgery, whilst in patients with metastatic disease, systemic therapy is employed with palliative intent. Accurate imaging is therefore central to the management of this disease.

Whilst computer tomography is useful in the initial localisation of NETs, nuclear imaging using tumour-specific radiolabelled receptor analogues or amine precursors are considerably more sensitive and specific methods for detecting NETs and their metastases. Five SSTR subtypes (1-5) have been identified in human tissues, with 70 – 90% of NETs expressing subtypes 2 and 5. Somatostatin analogues, such as octreotide, bind with high affinity to SSTR2 and SSTR5, and with varying affinity to SSTR3 and 4. When chelators such as diethylenetriamine pentaacetic acid (DTPA) or 1,4,7,10-tetraazacyclododecane-*N, N', N'', N'''* – tetraacetic acid (DOTA) are coupled to these analogues, they can be labelled with [¹¹¹In] or [^{99m}Tc] for scintigraphy in order to stage NETs. Furthermore, positive uptake on these scans will predict the likelihood of patients responding to therapy utilising radiolabelled somatostatin analogues. Currently, [¹¹¹In]-DTPA-octreotide SRS is the clinical gold standard for the imaging of these tumours, however there is an emerging clinical trend for the use of PET based on improved sensitivity and specificity.

In a review of pooled data from over 1200 patients, [¹¹¹In]-DTPA-octreotide SRS showed a median detection rate of 89% (range 67% to 100%) and a median sensitivity of 84% (range 57% - 93%)³. Whilst SRS is accurate, false positive results can be seen from the presence of inflammatory conditions that can be associated with an increase in SSTR expression such as in Crohn's disease⁴. Furthermore, NETs that are either too small or do not express high levels of SSTRs will not be detected. Other reasons for scan failure include low signal in areas of high background activity such as the liver and low spatial resolution.

Acquisition time is also prolonged, up to 48hours, making it inconvenient for both patients and nuclear medicine departments. Therefore, there is clearly a need to develop more accurate imaging techniques. The utility of PET imaging for visualising NETs has been highlighted with the development of [68Ga]-labelled somatostatin analogues. PET has superior physical characteristics compared to SRS including spatial resolution, sensitivity and quantification, and [68Ga]-labelled ligands also show higher affinity for SSTR 2 and 5 and more rapid clearance from the blood compared with [111-In]-labelled tracers, with images being obtained 60-90min following tracer injection. Furthermore, the radiation dose is lower using these tracers.

Preclinical and clinical studies have described the use of a number of analogues including DOTA-Tyr³ octreotide (DOTA-TOC), DOTA-Tyr³,Thr⁸octreotide (DOTA-TATE) and DOTA-1-Nal³-octreotide (DOTA-NOC) in the imaging of NETs ⁵⁻⁸. [¹⁸F]-Fluorodeoxyglucose (FDG)-PET has been extensively studied in NETs however the sensitivity of this imaging technique is low, 25 to 73%, because of the relatively low metabolic activity of NETs, making [¹⁸F]-FDG-PET not suitable for the routine clinical imaging, with its role currently limited to the visualisation of poorly differentiated tumours. Imaging with [⁶⁸Ga]-DOTA-TOC PET has been reported to be more sensitive than [¹⁸F]-FDG PET in patients with primary or recurrent NETs ⁹. Furthermore, clinical studies comparing [⁶⁸Ga]-DOTA-TOC PET with [¹¹¹In]-octreotide scintigraphy suggest that [⁶⁸Ga]-DOTA-TOC PET is more sensitive than SRS in detecting NETs as a result of greater signal-to-background contrast ^{10, 11}. Currently it is unclear which [⁶⁸Ga] tracer - DOTA-TOC, DOTA-TATE or DOTA-NOC - is the best and there is no consensus for their use partly due to lack of a robust supply mechanism for the radiotracers for clinical trials. It is clear, however, that the sensitivities of these tracers are better than SRS due to use of PET.

[figure not shown]
The main limitations with [⁶⁸Ga]-DOTA-analogues PET are the requirement for an on-site Gallium generator for tracer manufacture resulting from the much shorter half life of [⁶⁸Ga] compared to [¹⁸F] tracers that can be shipped easily to several sites and the low throughput of such generators, the poorer resolution of [⁶⁸Ga] compared to [¹⁸F] and the paucity of clinical grade GMP radiotracer for large multi-centre trials. We, therefore, sought to develop a fluorine-18 labelled octreotate analogue which can be effectively used to image NETs by employing a versatile two-step GMP-compatible click chemistry method; embodied in the design of these fluorinated analogues, strategies to improve tumour uptake and systemic PK ¹². Fluorinated somatostatin analogues have been previously developed due to their superior physical properties for PET imaging, however, their clinical utility have been limited by high background uptake making it very difficult to visualise tumours particularly those within the liver, the main site of metastatic disease. We have developed a novel [¹⁸F] labelled somatostatin analogue with improved *in vivo* kinetics compared to previously published [¹⁸F] labelled analogues.

5.1 [¹⁸F]-FET-βAG-TOCA-PET

We have developed a novel [¹⁸F]fluoroethyl triazole labelled [³Tyr]Octreotate analogue, [¹⁸F]-FET-βAG-TOCA, that has been shown to have more favourable kinetics compared to other fluorinated somatostatin analogues and [⁶⁸Ga]-DOTATATE *in vivo*^{12, 13}. We propose to transition [¹⁸F]-FET-βAG-TOCA-PET into humans within 2 cohorts of patients. Patients in cohort 1 will undergo ‘whole body dynamic PET scanning’ with assessment of PK and safety. We will then use this information to develop an optimal ‘whole body static PET scanning’ protocol that will be used for patients in cohort 2. We will directly compare the sensitivity and specificity of [¹⁸F]-FET-βAG-TOCA-PET to [⁶⁸Ga]-DOTATATE PET/CT, in the accurate localisation of NETs. It is anticipated that this novel tracer will eventually be the new standard in the imaging of these tumours.

Figure 1. Structure of βAG-TOCA.

Structural Formula

[figure not shown]
Molecular Formula

Molecular Weight

$C_{59}H_{76}FN_{15}O_{15}S_2$

1317.46 g.mol⁻¹

Figure 2. Flow Diagram for the synthesis of β AG-TOCA.

5.2 Rationale and evidence to date

NETs have a high density of SSTRs, in particular SSTR 2, on their cell surface. This characteristic allows the use of labelled somatostatin analogues to visualise these tumours. We developed five structurally-related [¹⁸F]fluoroethyltriazole-[Tyr³]octreotate analogues with suitable PK for PET imaging: [¹⁸F]-FET-G-PEG-TOCA, [¹⁸F]-FETE-PEG-TOCA, [¹⁸F]-FET-G-TOCA, [¹⁸F]-FETE-TOCA, and [¹⁸F]-FET- β AG-TOCA. To select a lead compound we compared the tissue PKs of each novel compound to the recently described [¹⁸F]-aluminium fluoride NOTA-octreotide ([¹⁸F]-AlF-NOTA) and [⁶⁸Ga]-DOTA-TOCA, a radiotracer widely used in the clinical assessment of NETs ¹⁴. All [¹⁹F]fluoroethyltriazole-[Tyr³]octreotate compounds retained high agonist binding affinity to SSTR2 *in vitro* (EC₅₀ of 4-19 nM versus somatostatin at 5.6 nM)¹².

Utilising the AR42J pancreatic cancer xenograft model, which expresses a high level of SSTR-2, dynamic PET imaging was performed following administration of each tracer. Tumour uptake was maximal with FET-G-TOCA, followed by FET- β AG-TOCA and [^{18}F]-AIF-NOTA, with the least tumour uptake seen with [^{68}Ga]-DOTATATE. Incorporation of polyethylene glycol (PEG) linkers to reduce non-specific protein interactions and increase circulation time, as exemplified by [^{18}F]- FET-G-PEG-TOCA and FETE-PEG-TOCA, resulted in reduced uptake in high SSTR2 expressing AR42J pancreatic cancer xenografts, and these were not taken forward. Whilst tumour uptake was maximal with [^{18}F]-FET-G-TOCA, its slow hepatic clearance meant that this was not taken forward, and [^{18}F]-FET- β AG-TOCA, which showed the lowest non-specific uptake in liver, was selected for further development (13). The specificity of [^{18}F]-FET- β AG-TOCA tumour uptake was illustrated through a number of experiments. Firstly, a radiolabelled scrambled peptide derived from [^{18}F]-FET- β AG-TOCA, [^{18}F]-FET- β AG-[W-c-(CTFTYC)K], did not show tumour uptake. Secondly, there was a 2-fold lower uptake of [^{18}F]-FET- β AG-TOCA in AR42J xenografts when mice were pre-treated with 10 mg/kg of unlabelled octreotide. Finally there was low uptake of [^{18}F]-FET- β AG-TOCA in low SSTR-2 expressing HCT116 xenografts.

The safety profile of [^{18}F]-FET- β AG-TOCA as a single microdose study in rats was assessed by a commercial GLP laboratory in accordance with MHRA/EMEA guidelines (see attached). There was no tracer (or precursor) related toxicity at 1000x the intended human dose. Rat radiation dosimetry studies, conducted by GE Healthcare are complete. The radiotracer showed a suitable organ dose profile. The new fluoroethyltriazole-[Tyr]³-octreotate radioligand, FET- β AG-TOCA, combines high specific binding with rapid target localization for high contrast PET imaging.

6. STUDY OBJECTIVES

6.1 Primary objective

- To determine the bidistribution of [^{18}F] following single i.v administration of [^{18}F]-FET- β AG-TOCA injection.
- To assess tumoural uptake of [^{18}F]-FET- β AG-TOCA

6.2 Secondary objectives

To assess efficacy of [^{18}F]-FET- β AG-TOCA PET/CT in patients with a histological diagnosis of NET and with measurable disease, who have and have not had [^{68}Ga]- DOTA-peptide imaging

6.3 Safety endpoints

The occurrence of one or more treatment-emergent adverse events (AEs) from administration of [¹⁸F]-FET-βAG-TOCA injection throughout the study period, and changes in serum biochemistry, haematology, coagulation, immunology, urinalysis, vital signs, ECG, injection site and physical examination findings.

7.1 Cohort 1

7.1.1 Primary

1. To determine the biodistribution (clearance from whole blood and plasma, and urinary excretion) of [¹⁸F] following single i.v. administration of [¹⁸F]-FET-βAG-TOCA injection in patients with a histological diagnosis of NET
2. To calculate the internal radiation dosimetry and the Effective Dose (ED)

7.1.2 Translational end-points

1. To assess the safety of [¹⁸F]-FET-βAG-TOCA
2. Assess expression of SSTR1-5 in biopsy specimens and compare with PET parameters

7.2 Cohort 2

7.2.1 Primary

1. To assess tumoural uptake of [¹⁸F]-FET-βAG-TOCA –PET/CT

7.2.2 Secondary

2. Compare diagnostic efficacy of [¹⁸F]-FET-βAG-TOCA in those patients who have had or not had or are due to have [⁶⁸Ga]-DOTA-peptide imaging. A power of $\geq 80\%$ has been chosen to conclude non-inferiority equivalence.

*Note** (All patients with a histological diagnosis of NET and lesion on CT is $\geq 1\text{cm}$ irrespective of whether they have had a [⁶⁸Ga]-DOTA-peptide scan or are waiting for one as part of their management will be included in study).*

3. Comparison of [¹⁸F]-FET-βAG-TOCA PET/CT scan and central review (nuclear medicine and radiology physician experts) of all imaging received by patient. (To account for any discrepancy that may exist between CT, [⁶⁸Ga]-DOTA-peptide imaging and [¹⁸F]-FET-βAG-TOCA PET/CT scan, then patients will be offered an MRI scan.

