10.3 Blinding

This is an open label study, therefore blinding is not applicable.

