11. STUDY PROCEDURES

Each patient will have one session of PET/CT scanning. Patients in cohort 1 will be required to have an overnight stay following their scan whilst those in cohort 2 will have up to a 70 minute scan and will be discharged home following the scan. All efficacy and safety measurements obtained during the

course of the study are summarised in the Study Schedule of Events in table 1 and 2.

Table 2. Study Schedule of Events for cohort 1.

| | -30 days screening | -30 to -5 min | -2 min | Dose | +2 min | +5 min | +10 min | +15 min | +30 min | +1 hour | +1 hour 30 min | +2 h 30 min | +4 hours | + 24 hours |
|-------------------------------------------------------------------|--------------------|---------------|--------|------|--------|--------|---------|---------|---------|---------|----------------|-------------|----------|------------|
| Informed Consent | • | | | | | | | | | | | | | |
| Entry Criteria | • | | | | | | | | | | | | | |
| Demographic Information | • | | | | | | | | | | | | | |
| Medical History | • | | | | | | | | | | | | | |
| Prior/Concomitant Medication | • | • | | | | | | | | | | | | |
| Physical Exam | • | • | | | | | | | | | | | | • |
| Injection Site Monitoring | | | • | | • | | • | | | | • | | • | • |
| Pregnancy Test | • | • | | | | | | | | | | | | |
| ECG ¹ | • | • | • | • | • | • | • | • | • | • | • | • | • | • |
| Pulse Oximetry ² | • | • | • | • | • | • | • | • | • | • | • | • | • | • |
| Vital Signs | • | • | • | | • | • | • | • | • | • | • | • | • | • |
| Blood (Serum Biochemistry, Haematology, Coagulation) ³ | • | • | | | | | | | • | | • | • | • | • |
| Urinalysis ⁴ | • | • | | | | | | | • | • | • | • | • | • |
| Pre-administration Events | | | | | | | | | | | | | | |
| Transmission Scan | | • | | | | | | | | | | | | |
| [¹⁸ F]-FET-βAG-TOCA injection | | | | • | | | | | | | | | | |
| Post-administration Events ⁵ | | | | | | | | | | | | | | |
| PET Imaging ⁶ | | | | | | | | | | | | | | |
| Blood and Plasma for Activity Counting | | | | | | • | • | • | • | • | • | • | | |
| Urine ⁴ for Activity Counting | | | | | | | | | | | | | | |

min=minutes

¹ Continuous ECG performed from -5 min to +15 min. Lead II may be used for continuous monitoring. 12-lead ECG should be recorded at the times indicated ECG should remain under continuous supervision and additional print outs obtained if any abnormality is detected

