14.1.4 Somatostatin receptor expression

SUV measures from [¹⁸F]-FET-βAG-TOCA PET/CT will be summarized by lesion. The correlation of SUV measures to ordinal measures of SSTR1-5 detected by IHC staining of the diagnostic biopsy (-, +, ++, +++) will be evaluated using non-parametric Kruskal-Wallis tests.

14.2 Cohort 2

Comparison will be made between FET-βAG-TOCA PET and the standard of a/cr somatostatin receptor imaging based on both a per-patient and per-lesion based analysis. Non-parametric McNemar test with Bonferroni correction for multiple comparisons will be used. The association between SSTR1-5 expression and imaging parameters obtained will be assessed. Data will be analyzed using SPSS 16.0 for Windows.

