14.2.1 Power and sample size determination

Power for the Wilcoxon signed-rank test is calculated by simulation using a truncated log-normal distribution parameterized according to Kabasakal et al.¹⁵ (median = 5, range = 1 to 25) to sample the total number of lesions in patients

across a range of samples. With a total of $N = 48$ patients assessed by both modalities, there will be 80% power to conclude non-inferiority equivalence if the two methods are equivalent ($\Delta = 0$).

The distributions of number of lesions detected by $[^{18}\text{F}]\text{-FET-}\beta\text{AG-TOCA}$ – PET/CT and by $[^{68}\text{Ga}]\text{-DOTA-peptide-PET/CT}$ will be summarized, and will be compared using the Wilcoxon signed-rank test with the pre-specified level of equivalence of $\Delta = 0.64$ and a one-sided alpha= 0.1.

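### Secondary endpoint 3 of cohort 2 compares the study scan with a central review that, as worded, includes the study scan, so agreement with it is liable to be overstated

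*Combined protocol and SAP*

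**What the plan says.** Section 7.2.2, endpoint 3, sets the study PET/CT against a "central review (nuclear medicine and radiology physician experts) of all imaging received by patient". The same item names CT, [68Ga]-DOTA-peptide imaging and the study scan as the sources between which discrepancies may arise. For those cases "then patients will be offered an MRI scan". It does not say which scans the panel reads, in what order, or how a lesion seen on one scan only is classified.

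Section 11 states: "Each patient will have one session of PET/CT scanning". Section 8.1 describes that scan as additional to routine staging. Section 10.3 states: "This is an open label study, therefore blinding is not applicable". No section describes a masked read.

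Section 5.1 sets the ambition: "We will directly compare the sensitivity and specificity of" the new tracer against [68Ga]-DOTATATE PET/CT. Section 14.2 plans per-patient and per-lesion comparisons with standard-of-care somatostatin receptor imaging: "Non-parametric McNemar test with Bonferroni correction for multiple comparisons will be used". Section 14.2.1 powers a comparison of lesion counts with [68Ga]-DOTA-peptide PET/CT. Section 14 gives no analysis for endpoint 3.

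**The concern.** A comparator used to judge a scan should be formed without that scan. If the panel has the study scan in front of it, a lesion seen nowhere else can enter the reference because of the study scan and then be scored as correctly detected. In the other direction, a panel that trusts the new scan may set aside a lesion that it missed. Both push agreement upward.

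The plan has no other lesion-level reference to correct this. The retrieved biopsy is the original diagnostic specimen and is used for SSTR1-5 staining, not to verify individual lesions. MRI is offered rather than required, only where scans disagree, and with no rule for how its result reclassifies a lesion.

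The stake is greatest for patients without a [68Ga] scan, where the panel may have little beyond CT and the study scan. An accuracy figure from this endpoint could be read as evidence of correct localisation when part of the agreement is built in.

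**Working it through.** **Plan's own figures.** Endpoint 3 has none. The only powered figure in cohort 2 concerns the lesion-count comparison: 48 "patients assessed by both modalities, there will be 80% power to conclude non-inferiority equivalence", with Δ = 0.64 "and a one-sided alpha= 0.1". It does not involve the central review. It also cannot be reproduced from the text, because the log-SD, the between-scan correlation and the scale of Δ are not given. With an assumed log-SD of ln5/2 and Δ on the count scale, simulated non-inferiority power ran from 30% (correlation 0) to 98% (correlation 0.95). The stated 80% is neither confirmed nor overturned, and nothing below depends on it.

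**Step 1. Does the review contain the study scan?** Section 7.2.2 says all imaging the patient received, and section 11 gives every patient the study scan. No section removes it or masks the panel. Inclusion therefore follows from the wording, although the plan never states it outright.

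**Step 2. Partial acceptance by the panel (assumed shares).** Let the panel accept a share w of the scan's false-positive calls and otherwise be correct.

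- Apparent specificity = Sp / [Sp + (1 − Sp)(1 − w)]. With Sp = 0.90: w = 0.25 gives 0.90/0.975 = 92.3%; w = 0.5 gives 0.90/0.95 = 94.7%; w = 0.75 gives 0.90/0.925 = 97.3%; w = 1 gives 100%.
- If the panel sides with the scan on a share w of its misses, apparent sensitivity = Se / [Se + (1 − Se)(1 − w)]. With Se = 0.80, the same shares give 84.2%, 88.9%, 94.1% and 100%.

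**Step 3. The extreme rule: any positive scan counts.** Ignoring false positives and taking scans as independent given truth, apparent sensitivity = s_F / [1 − (1 − s_F)(1 − s_O)], where s_F is the study scan and s_O the other imaging.

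- (0.80, 0.70): 0.80/0.94 = 0.851
- (0.80, 0.85): 0.80/0.97 = 0.825
- (0.85, 0.90): 0.85/0.985 = 0.863

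**Step 4. Including versus simply excluding the scan, with false positives allowed.** Assumed: half of candidate sites are tumour; the study scan has sensitivity 80% and false-positive rate 10%; other imaging has sensitivity 84% (section 5 quotes that median for scintigraphy, range 57% to 93%) and false-positive rate 5%.

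- Study-scan positives: 0.5×0.80 + 0.5×0.10 = 0.45. True PPV = 0.40/0.45 = 88.9%.
- Reference including the scan, any positive: 0.5(1 − 0.20×0.16) + 0.5(1 − 0.90×0.95) = 0.5565. Apparent sensitivity = 0.45/0.5565 = 80.9%. Specificity and PPV are 100% by construction.
- Reference from other imaging only: 0.5×0.84 + 0.5×0.05 = 0.445. Positive on both: 0.336 + 0.0025 = 0.3385. Negative on both: 0.016 + 0.4275 = 0.4435.

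| | True | Scan included | Scan excluded, unmatched lesions counted false |
|---|---|---|---|
| Sensitivity | 80% | 80.9% | 0.3385/0.445 = 76.1% |
| Specificity | 90% | 100% | 0.4435/0.555 = 79.9% |
| PPV | 88.9% | 100% | 0.3385/0.45 = 75.2% |

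The last two columns are also what results from counting the study-scan-only lesions (0.45 − 0.3385 = 0.1115 of sites) as all true or all false.

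**Step 5. Range.** With study-scan sensitivity 70–90%, its false-positive rate 5–20%, other-imaging sensitivity 57–93% and tumour share 50–80%, the any-positive reference always gave higher apparent sensitivity than the excluding reference, by about 1 to 15 points. It does not always exceed the truth: a true 90% reads 0.50/0.5645 = 88.6% with the other Step 4 inputs unchanged.

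**The case against.** The strongest reply is that the endpoint may mean the study scan against the rest of the work-up. Section 8.1 treats the study scan as an addition to routine staging, and the sentence naming all three modalities describes when MRI is offered, not what the panel reads. The body of the cohort 2 summary in section 4.2 was not readable in the text available and might settle this. The reading is possible, and inclusion remains an inference. But no readable section says so, and a panel following the words as written would read every scan.

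A second reply is that excluding the scan penalises a tracer that sees more. This stands against simple exclusion: in Step 4 it gives 76.1%, 79.9% and 75.2% against true values of 80%, 90% and 88.9%. Exclusion is sound only if unmatched lesions are not automatically called false.

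A third is that endpoint 3 names no accuracy measure, and that the section 5.1 sentence on sensitivity and specificity concerns the [68Ga] comparison. That is correct. The concern attaches to agreement with the review and to any accuracy figure later derived from it.

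A reader might also infer that this is the only endpoint not tied to the [68Ga] scan, or the only one for patients without it. The documents do not support that. Endpoint 2 covers patients with and without [68Ga] imaging, although it names no comparator for the latter. Section 14.2 compares with standard-of-care somatostatin receptor imaging, which is a wider term.

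**Conclusion.** The point holds for secondary endpoint 3 of cohort 2. As worded, the study scan can help define its own comparator, so agreement is liable to be overstated, most clearly for PPV and specificity. The conclusion rests on the plain sense of all imaging and on the absence of any exclusion, masking or other lesion-level reference. The size is unknown because the plan gives no panel rule; the figures above illustrate assumed rules and accuracies and do not estimate the bias in this trial.

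Three stronger readings should be resisted. The trial's efficacy evidence as a whole is not compromised in this way: the primary uptake endpoint, the standard-of-care comparison in section 14.2 and the powered lesion-count comparison do not refer to the central review. PPV would not necessarily read 100%: that needs a panel accepting every lesion seen on any scan, which expert review does not imply. Nor is sensitivity certain to be overstated, as Step 5 shows.

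For a secondary endpoint in a Phase 1 study, this should be corrected but does not undermine the trial.

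**What to change.** Amend endpoint 3 so that the same expert panel first reviews all imaging other than the study scan (CT, [68Ga]-DOTA-peptide PET and MRI where done), records its lesion list, and locks it before the study scan is shown. Use the locked review as the comparator.

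Report lesions seen only on the study scan as unconfirmed, counted neither as true nor as false positives. Reclassify them only where MRI, or other imaging read without the study scan, confirms or refutes them. Present results with the remaining unconfirmed lesions counted each way as bounds. In the Step 4 example, before any MRI, these would be 76.1–80.9% for sensitivity, 79.9–100% for specificity and 75.2–100% for PPV. The bounds cover only the unresolved lesions. They do not correct errors in the other imaging or false calls shared by all scans, so the truth can lie outside them: the true 90% sensitivity in Step 5 exceeds its upper bound of 88.6%.

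Add a short paragraph to section 14.2 naming the measures for endpoint 3 and this rule. If section 4.2 or a separate reading manual already keeps the study scan out of the review, say so in section 7.2.2.

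The cost is a reordered read and one CRF page, with no added readers or scans. The reported figure may be less favourable or wider, and some lesions will stay unresolved where MRI is not done.
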